#### 5.0 ANALYSIS SETS

## 5.1 All Subject Analysis Set

The 'All Subject Analysis Set' will include all screened subjects, including those who did not meet the study entry criteria and/or did not receive any study drug. This data set will only be used for disposition summaries.

## 5.2 Enrolled Subject Analysis Set

All subjects who sign an informed consent form (ICF) and meet all eligibility criteria as assessed by the investigator and sponsor. In addition, each subject who signs the ICF is assigned a unique identification (ID) number that reflects the study center number assigned to the investigator and the subject at that site.

## 5.3 Efficacy Analysis Set

The Efficacy Analysis Set will include all subjects who receive any amount of study drug. Efficacy analyses will be based on the actual treatment received on Cycle 1 Day 1, which should be the assigned cohort. The overall response rate (ORR) and DCR analysis will be based on subjects who are in the Efficacy Analysis Set and who had disease assessment at baseline and at least 1 follow-up disease assessment or subjects who died or stopped treatment before the first scheduled disease assessment due to clinical progression or toxicity.

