Note: Other gene aberrations that in the investigator's opinion may confer sensitivity to ASTX029 may be included in Cohort F after obtaining approval from the Sponsor's medical monitor.

For each potential subject, there is an up to 21-day screening and eligibility assessment period before enrollment; the first dose of study treatment will be administered on Cycle 1 Day 1 (C1D1). Subjects will continue to receive their assigned treatments throughout the study until the occurrence of disease progression, death, or unacceptable treatment-related toxicity; they elect to discontinue study treatment or withdraw consent to continue study participation; or until the study is closed by the sponsor.

Study visits will take place weekly during Cycles 1 and 2 and less frequently thereafter (see Table 11 and Table 12 for the complete schedules of events for the Regimen 1 and Regimen 2, respectively). Serial blood samples will be collected for PK and biomarker analyses at specified time points. If a formalin-fixed paraffin-embedded (FFPE) archived tumor biopsy is available, it will be obtained for use in this study during screening. In addition, in Phase 1 Part A and Phase 2, fresh tumor biopsies are optional during screening and posttreatment during Cycle 2. In

Phase 1 Part B, fresh tumor biopsies are mandatory during screening and posttreatment during Cycle 2.

Upon permanent discontinuation of study treatment, there is a Treatment Termination (Tx Term) visit and a 30-day (± 5 days or within 3 days before starting new treatment) Safety Follow-up visit. Subjects who remain on study after the 30-day Safety Follow-up visit will be contacted periodically by telephone for collection of long-term health status information.

Tolerability and safety of study treatment will be evaluated throughout the study by collection of clinical and laboratory data. Antitumor response will be assessed according to standard Response Evaluation Criteria in Solid Tumors (RECIST) v1.1 using computed tomography (CT) or magnetic resonance imaging (MRI) scans. Subjects whose disease is not measurable using RECIST v1.1 will be evaluated using another appropriate method.

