5.2. Inclusion Criteria

To be eligible for the study, subjects must fulfill all of the following inclusion criteria:

- 1. Able to understand and comply with the study procedures, understand the risks involved in the study, and provide written informed consent before any study-specific procedure is performed.
- 2. Men or women 18 years of age or older.
- 3. Subjects with histologically or cytologically confirmed advanced solid tumors that are metastatic or unresectable, who are refractory or have relapsed after treatment with available therapies or for whom standard life-prolonging measures or approved therapies are not available. In Phase 1 Part B and in the Phase 2 portion of the protocol, subjects must also have documented gene alterations in the MAPK pathway as detailed in Section 4.1.1, Section 4.1.2, and Table 2.
- 4. In Phase 1 Part B of the protocol, subjects must have disease lesions that are amenable to biopsy.
- 5. In the Phase 2 portion of the protocol, subjects must have measurable disease according to Response Evaluation Criteria in Solid Tumors (RECIST) v1.1.
- 6. Eastern Cooperative Oncology Group performance status 0 to 2.
- 7. Acceptable organ function, as evidenced by the following laboratory data:
 - a. AST and alanine aminotransferase (ALT) $\leq 2 \times$ upper limit of normal (ULN) or ≤ 3 ULN in the presence of liver metastases.
 - b. Total serum bilirubin $\leq 1.5 \times ULN$.
 - c. Absolute neutrophil count (ANC) \geq 1500 cells/mm³.
 - d. Platelet count $\geq 100,000$ cells/mm³.
 - e. Calculated creatinine clearance (by the standard Cockcroft-Gault formula) of $\geq 50 \text{ mL/min}$ or glomerular filtration rate of $\geq 50 \text{ mL/min}$.

- 8. Women of child-bearing potential (according to recommendations of the Clinical Trial Facilitation Group [CTFG]; see below* for details) must not be pregnant or breastfeeding and must have a negative pregnancy test (urine or serum as required by local regulations) within 24 hours before the first dose of study treatment. Women of child-bearing potential must agree to the following during the treatment period and for at least 32 days (approximately 5 half-lives of ASTX029 or metabolite plus 30 days) after receipt of last dose of study treatment:
 - a. Refrain from donating eggs (ova, oocytes) for the purpose of reproduction.

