- Lesions that meet the criteria for radiographically defined simple cysts should not be considered as malignant lesions (neither measurable nor nonmeasurable) since they are, by definition, simple cysts.
- 'Cystic lesions' thought to represent cystic metastases can be considered as measurable lesions, if they meet the definition of measurability described above. However, if noncystic lesions are present in the same subject, these are preferred for selection as target lesions.

Lesions With Prior Local Treatment

Tumor lesions situated in a previously irradiated area, or in an area subjected to other loco-regional therapy, are not considered measurable unless there has been demonstrated progression in the lesion.

Specifications by Methods of Measurements

Measurement of Lesions

All measurements should be recorded in metric notation, using calipers if clinically assessed. All baseline evaluations should be performed as close as possible to the treatment start and NEVER more than 21 days before the beginning of the treatment.

Method of Assessment

The same method of assessment and the same technique should be used to characterize each identified and reported lesion at baseline and during follow-up. Imaging-based evaluation should always be done rather than clinical examination unless the lesion(s) being followed cannot be imaged but are assessable by clinical exam.

CT, MRI: CT is the best currently available and reproducible method to measure lesions selected for response assessment. This guideline has defined measurability of lesions on CT scan based on the assumption that CT slice thickness is 5 mm or less. When CT scans have slice thickness greater than 5 mm, the minimum size for a measurable lesion should be twice the slice thickness. Magnetic resonance imaging (MRI) is also acceptable in certain situations (eg, for body scans).

Tumor Response Evaluation

Assessment of Overall Tumor Burden and Measurable Disease

To assess objective response or future progression, it is necessary to estimate the overall tumor burden at baseline and use this as a comparator for subsequent measurements. In this study, only subjects with measurable disease at baseline should be included in the study.

Baseline Documentation of 'Target' and 'Nontarget' Lesions

When more than 1 measurable lesion is present at baseline, all lesions up to a maximum of 5 lesions total representative of all involved organs should be identified as target lesions and will

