## 7.5 Efficacy Variables and Analyses

Efficacy analyses will be based on the Efficacy Analysis Set (Section 5.3). Efficacy variables will be summarized using descriptive statistics. No comparison between treatment sequences will be performed.

Anti-tumor response is based on Response Evaluation Criteria in Solid Tumors (RECIST) v1.1 (Eisenhauer et al 2009). The details of RECIST v1.1 evaluation of responses can be found in protocol Appendix 3. The principal investigator assessment of RECIST v1.1 response will be analyzed.

Table 1 provides a summary of the overall response status calculation at each time point for subjects who have measurable disease at baseline. Details of complete response (CR), partial response (PR), progressive disease (PD), and stable disease (SD) assessments for Target and Nontarget Lesions are provided in Appendix 3 of the protocol.

Table 1: Summary of Overall Assessment of Response					
Time Point Response: Subjects with Target (±Nontarget) Disease					
Target Lesions	Nontarget Lesions	New Lesions	Overall		

Target Lesions	Nontarget Lesions	New Lesions	Overall Assessment of Response
CR	CR	No	CR
CR	Non-CR/Non-PD	No	PR
CR	Not evaluated	No	PR
PR	Non-PD or not all evaluated	No	PR
SD	Non-PD or not all evaluated	No	SD
Not all evaluated	Non-PD	No	NE
PD	Any	Yes or No	PD
Any	PD	Yes or No	PD
Any	Any	Yes	PD

CR=complete response, NE=inevaluable, PD=progressive disease, PR=partial response; SD=stable disease.

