## 7.5.1 Overall Response and Disease Control Rate

The ORR will be calculated as the number of evaluable subjects whose best response is CR or PR, divided by the total number of subjects evaluable for ORR analysis (Section 5.3). The DCR will be calculated as the number of subjects whose best response is CR, PR, or SD, divided by the total number of subjects evaluable for DCR analysis (Section 5.3). The 90% Clopper-Pearson CIs for the ORR and DCR will be provided.

Best response for a subject is defined as the best overall response from all post baseline assessments of a subject in the study. When SD is believed to be the best response, it must also meet the protocol-specified minimum time from baseline (6 weeks). If the minimum time is not met when SD is otherwise the best time point response, the subject's best response depends on the subsequent assessments.

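### Phase 1 ORR counts subjects without measurable disease, who cannot reach PR, and the plan does not say how they count for DCR

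*SAP*

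**What the plan says.** **Denominator.** SAP Section 5.3 and Protocol Section 11.2.2 define the ORR and DCR set in the same way. It holds treated subjects "who had disease assessment at baseline and at least 1 follow-up disease assessment", together with those who died or stopped treatment before the first scheduled assessment because of clinical progression or toxicity. SAP Section 7.5.1 divides the CR and PR count by this set ("divided by the total number of subjects evaluable for ORR analysis"). The DCR numerator is "the number of subjects whose best response is CR, PR, or SD", over the same set. On precision it says "The 90% Clopper-Pearson CIs for the ORR and DCR will be provided".

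**Entry.** Criterion 5 in Protocol Section 5.2 reads "In the Phase 2 portion of the protocol, subjects must have measurable disease according to Response Evaluation Criteria in Solid Tumors". No criterion asks for measurable disease in Phase 1; criterion 4 asks only that Part B lesions be amenable to biopsy. Protocol Section 4.1.2 adds "Subjects whose disease is not measurable using RECIST v1.1 will be evaluated using another appropriate method", and Section 9.1 repeats the provision without naming a method. Appendix 3 says the opposite: "only subjects with measurable disease at baseline should be included in the study".

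**Response rules.** SAP Section 7.5 states "Table 1 provides a summary of the overall response status calculation at each time point for subjects who have measurable disease at baseline". Protocol Table 14 has the same scope. In Appendix 3, PR and SD are judged on the sum of target-lesion diameters. Non-target disease has three categories: CR, Non-CR/Non-PD and PD. SAP Section 7.5 analyses the investigator's RECIST v1.1 assessment.

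**The concern.** A Phase 1 subject with only non-target disease can satisfy SAP Section 5.3, because Protocol Section 9.4.8 accepts other evaluation methods, including tumor markers, as a disease assessment. That subject then sits in the ORR denominator with no access to PR, and in the DCR denominator with a result that the plan does not classify.

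DCR is a listed secondary endpoint, and Protocol Section 11.6 applies every efficacy endpoint to Part A and to the Part B cohorts. Two things are at stake:

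- A Phase 1 ORR set beside a Phase 2 ORR would mix two populations, since Phase 2 requires measurable disease. SAP Section 7.0 lists a layout that shows Phase 1A, Phase 1B and Phase 2 together.
- DCR for these subjects would depend on how each investigator or programmer fills a gap in the rules, in an open-label study without central reading.

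**Working it through.** **1. The plan's own figures.** Part B uses 14 subjects for a 90% chance of seeing at least one adverse reaction of 15% incidence: 1 - 0.85^14 = 0.897, as stated. The Phase 2 Simon design (continue at 2 or more of 10, reject at 6 or more of 29) gives an exact one-sided alpha of 0.047 at 10% and power of 0.805 at 30%, also as stated. Neither figure depends on this point.

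**2. Where a non-target-only subject can go.**

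| Category | Defined without target lesions? | Enters ORR | Enters DCR |
|---|---|---|---|
| CR | Yes (Appendix 3, non-target CR) | Yes | Yes |
| PR | No (needs a target-lesion sum) | Unreachable | Unreachable |
| SD | No (needs a target-lesion sum) | Does not apply | No rule |
| Non-CR/Non-PD | Yes, but not mapped to SD or disease control | No | Undefined |
| PD | Yes | No | No |

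**3. Effect on ORR.** Let n be the denominator, m the number without measurable disease, f = m/n, and R the responders among measurable subjects. If no non-measurable subject has a CR:

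ORR(all) = R/n = [R/(n - m)] x (1 - f)

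For an assumed measurable-disease ORR of 30%, f of 10%, 20% and 30% gives 27%, 24% and 21%.

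**4. Illustration.** Assumptions: n = 14, R = 3, and 7 measurable subjects with disease control. The documents give none of these as response data. The 14 is the Part B safety sample size, and the response set could be smaller. ORR(all) is 3/14 = 21.4% (90% Clopper-Pearson interval 6.1 to 46.6). DCR with every non-measurable subject counted as uncontrolled is 7/14 = 50.0% (26.4 to 73.6).

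| m | f | ORR, measurable only (90% CI) | DCR, measurable only | DCR, all m counted as controlled |
|---|---|---|---|---|
| 1 | 7.1% | 3/13 = 23.1% (6.6 to 49.5) | 7/13 = 53.8% | 8/14 = 57.1% |
| 2 | 14.3% | 3/12 = 25.0% (7.2 to 52.7) | 7/12 = 58.3% | 9/14 = 64.3% |
| 3 | 21.4% | 3/11 = 27.3% (7.9 to 56.4) | 7/11 = 63.6% | 10/14 = 71.4% |
| 4 | 28.6% | 3/10 = 30.0% (8.7 to 60.7) | 7/10 = 70.0% | 11/14 = 78.6% |

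DCR over all 14 lies below the measurable-only rate if these subjects count as uncontrolled, and above it if they all count as controlled. The plan does not choose between the two.

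**5. The exception for ORR.** One non-target CR gives 4/14 = 28.6%, above the measurable-only rate for m of 1 to 3 and below it for m = 4. The factor (1 - f) is therefore the largest dilution, not a certain one.

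**The case against.** The strongest reply is that nothing in the plan scores these subjects as failures. The two response tables are limited to measurable disease and are silent on everyone else. The SAP analyses what the investigator recorded, and an investigator following a subject by the permitted other method might enter SD, which would count in DCR. This stands for DCR. A reader might infer that both rates are understated; the documents support no such general statement, because the DCR coding is open and a non-target CR can enter either numerator. For ORR the reply is weaker. PR is a target-lesion measure, so a PR recorded by another method would fall outside the RECIST v1.1 definition that the SAP says it analyses.

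A second reply is that Appendix 3 restricts the study to measurable disease, so the situation cannot arise. If that sentence governed entry, this would be right. But the eligibility list is in Section 5.2, where the requirement is tied to Phase 2, and Sections 4.1.2 and 9.1 would serve little purpose otherwise. The contradiction is itself a defect.

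A third reply concerns consequence, and it stands. A reader might infer that dose selection was distorted. Protocol Section 7.3 records that the RP2D is already set, and the RDE and RP2D decisions draw on all safety, PK, biomarker and activity data rather than on this SAP derivation. Phase 1 activity rates are descriptive, and no formal comparison of ORR or DCR across doses or phases is planned.

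**Conclusion.** The point holds for the descriptive Phase 1 rates and should be corrected before those tables are produced. As written, the Phase 1 ORR denominator admits subjects who cannot reach PR. The rate is diluted by up to (1 - f) and differs in basis from Phase 2. For DCR the defect is an undefined rule, not a bias of known sign.

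The size is unknown, since f appears nowhere in the documents. In the illustration the ORR shift runs from 1.6 points (23.1 - 21.4, before rounding) at m = 1 to 8.6 points at m = 4, well inside intervals about 40 points wide or more.

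This rests on two assumptions: that criterion 5, not the Appendix 3 sentence, governed Phase 1 entry, and that at least one Phase 1 subject lacked measurable disease. The Phase 2 primary ORR and the Simon design are unaffected, and no effect on the RDE or RP2D decision is shown.

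**What to change.** - In SAP Sections 5.3 and 7.5.1, base Phase 1 ORR on subjects with RECIST v1.1 measurable disease at baseline, which is the Phase 2 basis.
- Add response rows for subjects with non-target disease only (CR, Non-CR/Non-PD, PD). State that Non-CR/Non-PD lasting at least the 6-week minimum already set for SD counts as disease control for DCR.
- Report the number of subjects without measurable disease in each Phase 1 cohort, and list any non-target CR among them, since it would fall outside the restricted ORR.
- Reconcile the Appendix 3 sentence with criterion 5 and Protocol Sections 4.1.2 and 9.1.

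The cost is SAP wording, a few extra response rows and one flag derived from the baseline lesion categories that Appendix 3 already requires. The downside is that ORR and DCR would have different denominators in Phase 1, which the tables must label, and ORR intervals would be slightly wider. Keeping one denominator and adding only the non-target rows would avoid this, but PR would remain unreachable for some of the subjects counted in ORR.

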The dose-escalation part of the study (Phase 1 Part A) follows a 3+3 study design, with a cohort size of either 3 or 6 evaluable subjects. Dose escalation will continue until an MTD is determined for each dosing regimen evaluated.

For Phase 1 Part B, a sample size of 14 evaluable subjects will ensure a 90% probability of observing at least 1 adverse reaction to treatment for any adverse reaction with a \geq 15% incidence. Evaluable subjects for Part B are all subjects who receive any amount of study drug.

For Phase 2, the sample size is based on a Simon's Optimal 2-stage design. Each cohort will enroll 10 subjects into the first stage. Should ≥ 2 first-stage subjects respond, an additional 19 subjects will be enrolled into the second stage. Therefore, up to 29 subjects will be used for each treatment cohort. The sample size, (10+19) 29, under this Simon's Optimal 2-stage design, will achieve a power of 80% to test the null hypothesis of ORRp₀ ≤ 0.1 at a 1-sided alpha of 0.05 assuming the response rate p₁ is 0.3. For Stage 2, the null hypothesis will be rejected if ≥ 6 responses are observed in a cohort of 29 subjects. For Phase 2 Cohort F (which will enroll patients with various tumor types and gene aberrations), the sponsor, with approval of the DSRC, may expand enrollment for a particular molecularly defined subpopulation in which the most number of responses are observed to 10 or 29 subjects under the same Simon's Optimal 2-stage design as for the other cohorts for better assessment of activity in that disease subgroup (Optional Cohort F Expansion). It is expected that no more than 2 subgroups will be expanded in this manner.

Efficacy:

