5.4.1. Discontinuation From Study Treatment

Subjects may permanently discontinue study treatment at any time (**note: subjects who experience disease progression while receiving ASTX029 should not remain on study treatment**). Subjects who discontinue study treatment will still continue study follow-up procedures until death, or until they withdraw consent or the study is closed. Investigators are encouraged to assess all subjects according to the study protocol even after discontinuation from study treatment. Possible reasons for discontinuation of study treatment include the following:

- Investigators can discontinue subjects from study treatment in case of unacceptable toxicity, non-compliance, disease progression requiring alternative therapy, or if the investigator determines it is in the subject's best interest.
- The Sponsor may require that a subject is discontinued from treatment for safety reasons or for noncompliance.

In all cases, the reason(s) for discontinuation from study treatment must be recorded in the source document and on the relevant page of the subject's electronic case report form (eCRF).

It is important to obtain protocol-specified follow-up information on any subject discontinued from study treatment. For subjects who discontinue study treatment, the investigator should review the follow-up procedures with the subject, including the number of visits, the specific procedures to be done, and the total length of the follow-up period. If at all possible, subjects should undergo all safety and preliminary clinical activity evaluations at the Tx Term visit (Section 9.4.13) and the 30-day Safety Follow-up visit (Section 9.4.14). Section 10 describes follow-up for AEs. At minimum, subjects should be followed up for safety until 30 days after the last dose of study treatment (see Section 10.3).

Subjects who agree to remain enrolled in the study after discontinuing study treatment and completing the 30-day Safety Follow-up visit will be contacted by telephone for health status information every 3 months until death, withdrawal of consent, or the end of study, whichever occurs first (see Section 9.4.15).

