5.4.3. Replacement of Subjects

Subjects will be replaced in this study as needed to achieve the planned number of evaluable subjects in each part of the protocol. See Section 11.1 for the definition of evaluable subjects.

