In Part B, one or more dose levels (and regimens) may be studied to supplement available safety, PK, and/or clinical activity data and to evaluate target engagement in firesh tumor tissue biopsies. A total of 14 evaluable subjects will be treated at each dose/regimen selected. If more than 1 dose/regimen is selected, subjects will be randomized in a 1:1 ratio. Subjects will have to meet the following molecular eligibility criteria: documented activating gene mutations in BRAF (BRAF V600 mutation or activating atypical non-V600 aberrations), Kirsten RAS (KRAS), NRAS, or Harvey RAS (HRAS). The RP2D decision by the DSRC will be based on all available PK, pharmacodynamic, safety, and preliminary activity data from all cycles (including the potential for late or cumulative toxicity). The RP2D could be the same or lower than the RDE.

The DSRC will advise when it is appropriate to proceed to Phase 2. The Phase 2 portion of the study will explore the preliminary single-agent antitumor activity of ASTX029 at the RP2D of the selected dosing regimen identified in Phase 1 Parts A and B in tumors characterized by gene aberrations in the MAPK signal pathway that may confer sensitivity to ASTX029. The Phase 2 part of the study will consist of the following 6 cohorts:

- Cohort A: NRAS-mutant melanoma.
- Cohort B: KRAS-mutant or KRAS-amplified non-small cell lung cancer (NSCLC).
- Cohort C: BRAF V600-mutant cancers (non-colorectal cancers).
- Cohort D: BRAF-fusion cancers.

- Cohort E: Gynecological cancers with alterations in the MAPK pathway.
- Cohort F: Tumors characterized by other gene aberrations that upregulate the MAPK signal pathway. In the Phase 2 part of the study, molecular eligibility will be based on the presence of documented gene aberrations in MAPK pathway.

For Phase 2, the sample size is based on a Simon's Optimal 2-stage design. Each cohort will enroll 10 subjects into the first stage of Simon's 2-stage design at the RP2D and the dosing regimen identified in Phase 1 Parts A and B. Should ≥2 first-stage subjects respond, an additional 19 subjects will be enrolled into the second stage. Therefore, up to 29 subjects will be enrolled into each cohort.

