### 4.0 SAMPLE SIZE

The dose-escalation part of the study (Phase 1 Part A) follows a standard 3+3 study design, with a cohort size of 3 or 6 evaluable subjects. Dose escalation will continue until the MTD for each regimen evaluated is determined. Evaluable subjects for dose-escalation decisions in Part A are those who have completed the first cycle and have received at least 85% of planned doses in the first cycle of treatment (or were not able to receive at least 85% of planned doses due to safety concerns). The final sample size of part A will depend on the assessed dose levels and occurrence of dose limiting toxicities.

For Part B (of Phase 1), a sample size of 14 evaluable subjects will ensure a 90% probability of observing at least 1 adverse reaction to treatment for any adverse reaction with a  $\geq$ 15% incidence. Evaluable subjects for Part B are all subjects who receive any amount of study drug.

For Phase 2, the sample size is based on a Simon's Optimal 2-stage design (Simon 1989). Each cohort will enroll 10 subjects into the first stage. Should  $\geq 2$  first-stage subjects respond, an additional 19 subjects will be enrolled into the second stage. Therefore, up to 29 subjects will be used for each treatment cohort. The sample size, (10+19), or 29, under this Simon's Optimal 2-stage design, will achieve a power of 80% to test the null hypothesis of ORR p0  $\leq 0.1$  at a 1-sided alpha of 0.05 assuming the response rate p1 is 0.3. For Stage 2, the null hypothesis will be rejected if  $\geq 6$  responses are observed in a cohort of 29 subjects. For Cohort F (which will enroll patients with various tumor types and gene aberrations [Protocol Table 2]), the sponsor, with approval of the DSRC, may expand enrollment to 10 or 29 subjects for a particular molecularly defined subpopulation in which the most number of responses are observed, under the same Simon's Optimal 2-stage design as for the other cohorts for better assessment of activity in that disease subpopulation (Optional Cohort F expansion). It is expected that no more than 2 subpopulations will be expanded in this manner.

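### The Phase 2 ORR drops, and apparently replaces, treated subjects who leave unassessed for reasons other than death, clinical progression or toxicity, so it overstates response among all treated subjects

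*SAP*

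**What the plan says.** SAP 5.3 and Protocol 11.2.2 build the Efficacy Analysis Set from everyone dosed, then narrow it for ORR and DCR. A subject counts if assessed at baseline and at least once later, or if among the "subjects who died or stopped treatment before the first scheduled disease assessment due to clinical progression or toxicity". SAP 7.5.1 uses that count as the denominator: responders are "divided by the total number of subjects evaluable for ORR analysis (Section 5.3"). PFS and OS keep every dosed subject (SAP 7.5.3).

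On replacement, Protocol 5.4.3 says: "Subjects will be replaced in this study as needed to achieve the planned number of evaluable subjects in each part of the protocol". It points to Section 11.1 for the meaning of evaluable, but that section defines the term only for Phase 1 Parts A and B. Protocol 4.1.2 counts Stage 1 of each Phase 2 cohort in evaluable subjects and gives the Stage 2 total simply as 29 subjects.

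The decision rule is fixed in counts. SAP 3.1: "Should ≥2 first-stage subjects respond, an additional 19 subjects will be enrolled into the second stage". Protocol synopsis: "the null hypothesis will be rejected if ≥ 6 responses are observed in a cohort of 29 subjects".

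No ORR in all treated subjects is planned. SAP 7.0 plans a listing of subjects left out of the efficacy analysis.

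**The concern.** A subject with no post-baseline assessment cannot be recorded as a responder. Each one removed from the denominator is a certain non-responder, so the bias relative to all treated subjects runs one way, upward. If that subject is also replaced by someone who can respond, the fixed cut-offs of 2 in 10 and 6 in 29 become easier to reach.

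Whether an unassessed subject stays in depends on the recorded reason for leaving, which is settled after treatment starts, in an open-label trial with investigator-assessed response. The protocol foresees reasons outside the retained list: withdrawn consent and loss to follow-up (Protocol 5.4.2), and, among reasons for stopping treatment, "non-compliance, disease progression requiring alternative therapy, or if the investigator determines" that stopping is in the subject's best interest (Protocol 5.4.1). At stake are the reported level of the primary Phase 2 endpoint, each cohort's decision to continue, and the final claim against a 10% response rate, in up to six cohorts.

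**Working it through.** **Inputs from the documents.** Null rate, power and alpha: "power of 80% to test the null hypothesis of ORRp₀ ≤ 0.1 at a 1-sided alpha of 0.05" (Protocol synopsis). Alternative: "1-sided alpha of 0.05 assuming the response rate p1 is 0.3" (SAP 4.0). Stage 1 has 10 subjects and continues on 2 or more responses; Stage 2 adds 19; the null is rejected on 6 or more of 29.

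**Input assumed.** d is the share of treated subjects excluded and replaced. The documents give no figure, so a range is shown.

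**Step 1: the plan's own figures.** The exact probability of rejecting at true rate p is

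R(p) = sum over x = 2 to 10 of P[Bin(10, p) = x] × P[Bin(19, p) ≥ max(0, 6 − x)].

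R(0.10) = 0.0471 and R(0.30) = 0.805. Both stated properties are reproduced. The chance of going on to Stage 2 under the null is 0.264. The slack below 0.05 is only 0.05 − 0.0471 = 0.0029.

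**Step 2: exclusion with replacement.** Excluded subjects are all non-responders. If ORR among all treated subjects is 0.10, ORR among those who count is 0.10/(1 − d), and the rule is in effect run at that rate.

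| d | ORR among evaluable, 0.10/(1 − d) | One-sided error R | Treated for 29 evaluable, 29/(1 − d) |
|---|---|---|---|
| 0% | 0.1000 | 0.047 | 29.0 |
| 1% | 0.1010 | 0.049 | 29.3 |
| 2% | 0.1020 | 0.051 | 29.6 |
| 5% | 0.1053 | 0.058 | 30.5 |
| 10% | 0.1111 | 0.071 | 32.2 |
| 15% | 0.1176 | 0.088 | 34.1 |
| 20% | 0.1250 | 0.110 | 36.2 |

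R reaches 0.05 at an evaluable rate of 0.1015, so d = 1 − 0.10/0.1015 = 0.015, or about 1.5%. At d = 10% the chance of passing Stage 1 under the null rises from 0.264 to 0.307.

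**Step 3: exclusion without replacement.** If the counts 2 and 6 are applied to the first 10 and 29 treated subjects, dropping a non-responder from the denominator does not change the number of responders. The error stays at R(0.10) = 0.0471 and only the reported percentage moves. Replacement together with fixed cut-offs is what raises the error.

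**Step 4: size of the shift in the estimate.** Take 6 responders among 29 evaluable subjects, with 3 more treated but excluded. The evaluable ORR is 6/29 = 20.7% (90% Clopper-Pearson interval 9.4% to 36.8%). The all-treated ORR is 6/32 = 18.8% (8.5% to 33.7%).

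**Step 5: power under an all-treated rule without replacement.** If 0.30 is the all-treated rate, power stays at 0.805. If it was meant for evaluable subjects only, the all-treated rate is 0.30 × (1 − d): R(0.285) = 0.766 at d = 5% and R(0.27) = 0.720 at d = 10%.

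**The case against.** A reader might infer that the trial fails to hold its 5% error rate. The documents do not support that. They define ORR on evaluable subjects, and for that quantity the error is 0.0471. Exceeding 0.05 requires the 10% null to refer to all treated subjects, which the plan does not say, and more than about 1.5% of them to be excluded and replaced.

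Replacement in Phase 2 is also less than explicit, because Section 11.1 gives no Phase 2 definition of evaluable. That is fair, but it leaves the trigger open. Protocol 5.4.3 covers every part of the study, and Protocol 4.1.2 counts Stage 1 in evaluable subjects.

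A reader might also infer that everyone who stops early for non-compliance or by investigator decision leaves the denominator. They do not. SAP 5.3 asks for one later assessment and does not require it to be on treatment. Protocol 5.4.1 continues follow-up after treatment stops, and SAP 7.5.1 takes best response from all post-baseline assessments. The excluded group is therefore mainly those who withdraw consent or are lost before the scan at the end of Cycle 2 (2 × 21 = 42 days). The most outcome-related early losses are already kept as non-responders. Nothing in the documents points to shares as high as 15% or 20%.

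Nor is the primary endpoint's set narrower than that of every secondary endpoint. DCR uses the same set and DOR covers responders only; PFS and OS are the wider ones.

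Finally, Phase 2 seeks preliminary activity, efficacy is summarised descriptively, and the planned listing would let someone rebuild an all-treated ORR. That lowers the stakes. It does not replace a prespecified figure.

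**Conclusion.** The point stands in conditional form. Following the plan biases the reported ORR upward relative to all treated subjects, because each excluded subject is a certain non-responder.

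For ORR among evaluable subjects the design holds 0.047. For ORR among all treated subjects, the one-sided error exceeds 0.05 once more than about 1.5% are excluded and replaced, which is fewer than one subject per full cohort on average (0.015 × 29 = 0.4). It is 0.058 at 5% and 0.071 at 10%.

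These figures rest on three assumptions: an assumed exclusion share, a 10% null read as applying to all treated subjects, and replacement actually being used in Phase 2. Without replacement, and with the counts applied to treated subjects, the error is unchanged and only the percentage rises. The direction of the bias is certain; its size cannot be fixed from the documents.

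**What to change.** In SAP 5.3 and 7.5.1, report ORR and DCR, with the 90% Clopper-Pearson interval already planned, in all treated Phase 2 subjects with measurable disease at baseline (required by inclusion criterion 5). Count subjects without a post-baseline assessment as non-responders. Make this the primary ORR, or at minimum a prespecified analysis shown beside the response-evaluable ORR. State for each cohort whether the 6-of-29 conclusion holds when no subject is replaced. Define evaluable for Phase 2 in Protocol 11.1 so that the replacement trigger in 5.4.3 is explicit.

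The cost is one extra table, a short change of wording in each document and a slightly lower reported ORR. If the 30% target was meant for evaluable subjects only, power under the all-treated rule is about 0.77 with 5% unassessed and 0.72 with 10%, against 0.805.

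Forbidding replacement outright and re-running the 2-of-10 decision on the first 10 treated is not proposed. It would contradict Protocol 5.4.3 and 4.1.2, need a protocol change, and could conflict with Stage 1 decisions already taken.
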